## 1.0 Background

Peripheral artery disease (PAD) is characterized by atherosclerotic obstruction of the arteries in the lower extremities and affects approximately 10% of individuals older than 65 years. Patients with symptomatic PAD experience walking impairment and declines in physical performance and quality of life. At the extreme end of the clinical spectrum, patients with critical limb ischemia (CLI) have ischemic pain at rest and develop nonhealing or gangrenous wounds that might necessitate limb amputation. These patients with severe PAD require comprehensive medical management and effective limb revascularization to augment tissue oxygenation, promote wound healing and reduce pain. Endovascular and surgical interventions are considered in patients with PAD who have developed lifestyle-limiting claudication no longer responsive to conservative therapy and CLI. Patients with symptomatic PAD receiving intensive evidence-based therapies undergo peripheral revascularization frequently, with approximately 1 in 5 (19.3%) undergoing procedures at 3 years. Despite major technological advances in surgical and endovascular care, a significant number of patients with severe PAD that undergo revascularization procedures are readmitted because of persistent symptoms and loss of patency. Restenosis occurs frequently, within the first year after an intervention. There remains an urgent need for adjunctive therapies that aid in the improvement of tissue blood flow and consequently relieve pain and improve functional capacity in these patients.

## 2.0 Rationale and Specific Aims

One emerging adjunctive therapy that has the potential to enhance the benefits of revascularization procedures for severe PAD is the application of intermittent pneumatic leg compressions (IPC). This is a non-invasive intervention, consisting of an air pump inside inflatable cuffs that are wrapped around the feet, ankles, and calves and worn for two hours daily. Every 20 second, the cuffs rapidly inflate, followed by rapid deflation. We and others have previously shown that exposure to IPC markedly enhances leg blood flow and vascular shear-stress in the arteries of the leg (2, 6, 7). Our preliminary work shows that 2 weeks of daily application of IPC enhances exercise tolerance in a model of PAD, in part by enhancing blood flow to collateral-dependent tissues (4). IPC has also been shown to reduce amputation rates in patients with CLI without a revascularization option. The objective of this *pilot* study is to establish evidence to support the validity of IPC in improving the outcome of lower-extremity revascularization for severe PAD. Our central hypothesis is that the treatment with IPC will lead to greater improvements in leg hemodynamics as compared to a sham device. As a result, we anticipate that patients treated with IPC will report less rest pain, have enhanced walking endurance and improved calf muscle oxygenation resulting in a subsequent improvement in quality of life. To test this hypothesis, we propose the following specific aim:

***SPECIFIC AIM:*** Determine the effects of IPC following revascularization in patients diagnosed with severe PAD.

Figure 1: Intermittent pneumatic compression device

Patients will be enrolled in the study approximately 3 months after the revascularization procedure and will be randomly assigned to one of two groups: IPC or placebo pump. Patients will receive a commercially available IPC device (ArtAssist, ACI Medical, San Marcos, CA) and will be asked to apply the treatment to both legs at home for 2 hours daily during 3 consecutive months. Prior to the onset of the treatment and 1 and 3 months after daily home-based IPC, we will assess patient's leg hemodynamics, rest pain, calf muscle oxygenation during exercise, walking endurance and quality of life. We expect beneficial changes in leg hemodynamics, reduced rest pain, increased levels of exercise tolerance, improved calf muscle oxygenation during exercise, and improved quality of life, (QOL) as assessed by responses to VascuQol and SF36 questionnaires. The ankle-brachial index (ABI), the toe-brachial index (TBI), and rest pain will be assessed on the leg undergoing the revascularization procedure and the opposite leg. Transcutaneous PO2 (TcPO2) and calf muscle oxygenation will only be assessed in the leg undergoing revascularization.

### **3.0 Inclusion/Exclusion Criteria**

#### **Inclusion criteria**

- 1) At least 18 years of age
- 2) Evidence of significant obstructive disease for one or multiple lower extremity arteries, as identified by prior ABI, TBI, CT angiography, ultrasound, or MR imaging
- 3) Completed endovascular or surgical revascularization of one or both lower extremities within the past 3 months ( $\pm$  14 days)

#### **Exclusion criteria**

- 1) Chronic kidney disease (eGFR <30 by MDRD or Mayo or Cockcroft-Gault formula)
- 2) Open and/or non-healing wounds in the areas covered by the IPC cuff
- 3) Inability to walk on the treadmill
- 4) Abnormal baseline treadmill stress test
- 5) Walking limited by a symptom other than PAD
- 6) Inability to independently and correctly position the IPC cuff on legs and feet
- 7) Presence of any clinical condition that makes the patient unsuitable to participate in the trial
- 8) Concern for inability of the patient to comply with study procedures and/or follow up (e.g., alcohol or drug abuse)
- 9) Acute deep vein thrombosis (DVT) either suspected or diagnosed
- 10) Uncontrolled infection
- 11) Increased pain with ArtAssist device operating or with worsening skin tissue condition
- 12) During episodes of inflammatory phlebitis or pulmonary embolism
- 13) When increased venous or lymphatic return is undesirable including presumptive evidence of congestive heart failure

## **4.0 Enrollment/Randomization**

Patients will be recruited by [name] and his associates at the Indiana University Health Methodist Hospital, Indiana University Health West Hospital and Indiana University Health Arnett. Patients that fulfill the inclusion criteria and are interested in participating in the protocol will receive detailed instructions about the experimental set-up and measurements and will be given a consent form. After providing consent, patients will be asked to complete the baseline assessment, including the assessment of leg hemodynamics, rest pain, calf muscle oxygenation during exercise, walking endurance and quality of life. Patients will be randomized into one of two groups: IPC (n=4) or placebo pump (n=4). Patients will receive an IPC device and will be asked to apply the treatment at home for 2 hours daily during 3 consecutive months. Outcomes will be reassessed 1 and 3 months after the onset of home-based treatment.

## **5.0 Study Procedures**

After enrollment, subjects will be asked to complete two experimental sessions for baseline testing. The procedures involved in each visit are listed on Table 1. Subjects will be asked to fast overnight and refrain from smoking or using alcohol for 4 hours prior to attending all experimental sessions. Subjects will be permitted to take their usual morning medication. Although fasting and refraining from tobacco, alcohol and exercise are desired for testing consistency, it will not be considered a protocol deviation if the subject does not follow these instructions prior to one of the study visits. On visit 1, demographic and anthropometric characteristics from participants will be initially recorded. Patients will be asked to report the pain in their legs using visual analog scale (VAS). The study coordinator will demonstrate how to operate the IPC pump on how to wear the legs cuffs. Participants will be given the opportunity to independently place the cuffs around their legs. Individuals that are unable to successfully complete this task without help will be excluded from the study. Participants will then perform a standard symptom-limited cardiopulmonary exercise test on a treadmill. A near-infrared spectroscopy (NIRS) system, which measures skeletal muscle oxygenation, will be placed on the calf of the most symptomatic leg. Participants with an abnormal baseline treadmill stress test, including signs of coronary ischemia and an exaggerated pressor response, will be excluded from the study. This session (Visit 1) will be performed at Methodist Hospital and is expected to last approximately 3 hours.

At least 72 hrs after visit 1, subjects will be asked to return for visit 2. Participants will be asked to lay supine and a member of the Vascular Access Team (VAT) will draw a blood sample (20 mL) from one antecubital vein in the arm. Next, participants will undergo the bilateral assessment of the ankle-brachial index (ABI), the toe-brachial index (TBI) and transcutaneous PO2 (TcPO2) following standard of care practices. Patients will be asked to report the pain in their legs using visual analog scale (VAS). Patients will then be escorted to the exercise testing lab to undergo a graded, symptom-limited cardiopulmonary exercise test on a treadmill as described for visit 1. At the end of the session, subjects will be asked to fill out two questionnaires to assess generic (36-item Short-Form Health Survey) and disease-specific (Walking Impairment Questionnaire) quality of life. Next, patients will be trained on how to operate the IPC pump on how to wear the cuffs and will undergo a 15-min practice treatment session. At the end of the practice session, participants will be trained on: 1) how to wash and care for the inflatable cuffs, 2) how to turn the pump on and off, 3) how to record usage time on a logbook. Participants will receive the ArtAssist device (ACI Medical Inc, San Marcos, CA, USA) for IPC application. This device applies compressions to both the calf and foot, at a pressure of 120 mmHg for 3 seconds

per cycle, and this continues for three cycles per minute with a 1-second delay between different segment inflation. Patients allocated to the control group will receive a sham device, that applies a pressure of 30 mmHg at the frequency specified above. Participants on both groups will be asked to apply the cuffs to both legs and use the device while seated for 2 hours daily for 3 months. This session (Visit 2) will be performed at IU's Methodist Hospital and is expected to last approximately 4 hours.

Patients in both groups will receive weekly telephone calls from the study coordinator to verify compliance and will receive a logbook to record their sessions. A timer built into the IPC unit, and inaccessible to patients, will also provide an estimate of the patients' compliance with the treatment regimen. The logbook is intended to assist the participant keep track of the daily treatments; it will not be a protocol deviation if the logbook is not returned at the end of the treatments. Compliance with daily treatment will be formally assessed and documented with the weekly phone call from the study team. A protocol deviation will occur when either 3 consecutive home treatments are not performed or when 8 or more home treatments are not performed during the 3-month treatment period.

Outcomes will be reassessed after 1 month of treatment (end of week  $4 \pm 7$  days) and at the completion of the intervention (end of week  $12 \pm 7$  days). The protocol for these outcome visits will be similar to visit 2 as detailed in the table below. To ensure that the chronic rather than the acute effects of IPC are investigated, participants will be asked to interrupt the treatment 48 hrs prior to the outcome sessions. Although interrupting the treatment 48 hours prior to the outcomes sessions is desired for testing consistency it will not be a protocol deviation if a subject does not interrupt the treatment as instructed.

Visit #	Time point	Procedures
1	Baseline	Consenting Rest pain measurement Demonstration of device operation and proper cuff placement Familiarization with Cardiopulmonary Treadmill test
2	Baseline	Blood draw ABI, TBI and TCPO 2 Rest pain measurement Cardiopulmonary Treadmill test Quality of life questionnaires Familiarization with treatment
3	1 month	Blood draw ABI, TBI and TCPO 2 Rest pain measurement Cardiopulmonary Treadmill test Quality of life questionnaires
4	3 months	Blood draw ABI, TBI and TCPO 2 Rest pain measurement Cardiopulmonary Treadmill test Quality of life questionnaires

**Table 1:** Study timeline and experimental procedures that will be performed on each session

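### Fasting before every session with morning medication permitted without exception: a patient on insulin or an insulin-releasing drug may take it unfed before a treadmill test

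*Combined protocol and SAP*

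**What the plan says.** The preparation rule is in the protocol, section 5.0 Study Procedures. It reads "Subjects will be asked to fast overnight and refrain from smoking or using alcohol for 4 hours prior to attending all experimental sessions", followed directly by "Subjects will be permitted to take their usual morning medication". The same paragraph then relaxes the preparation rules. It begins "Although fasting and refraining from tobacco, alcohol and exercise are desired for testing consistency" and goes on to say that "it will not be considered a protocol deviation if the subject does not follow these instructions prior to one of the study visits".

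Exercise is part of each session:

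- Visit 1: "Participants will then perform a standard symptom-limited cardiopulmonary exercise test on a treadmill". Table 1 calls this familiarization.
- Visit 2: after the blood draw, the limb measurements and the pain rating, "Patients will then be escorted to the exercise testing lab to undergo a graded, symptom-limited cardiopulmonary exercise test on a treadmill". This session "is expected to last approximately 4 hours".
- Visits 3 and 4: "The protocol for these outcome visits will be similar to visit 2 as detailed in the table below". Table 1 lists the treadmill test at both.

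The protocol text available does not mention diabetes, insulin, glucose, a snack or a dose adjustment. The exclusion criteria in section 3.0 do not remove patients on glucose-lowering drugs. The treadmill paragraph under Potential risks to subjects names staggering, diaphoresis and dizziness among possible effects, but not low glucose.

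**The concern.** Fasting before a test and allowing regular medication are both ordinary instructions, and for most drugs they combine without difficulty. Insulin and insulin-releasing drugs are the exception, because the usual morning dose assumes that food will follow. Here the dose may be taken with no food, and a symptom-limited exercise test comes next. At visit 2, and by reference at visits 3 and 4, the test is also preceded by a series of other measurements.

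What is at stake is an avoidable episode of low glucose during or around the test. Its signs can resemble the treadmill effects already listed, so staff who have not been alerted to it could attribute them to exertion. The point concerns patient safety and makes no claim about an outcome or the analysis.

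**Working it through.** The plan states no figure on this point, so the check is mainly a reading of the text, followed by a count of scheduled tests.

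**Reading the instructions together (section 5.0)**

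1. Fasting: overnight, for all subjects, before all sessions.
2. Medication: the usual morning drugs are allowed, with no class excepted.
3. Exercise: a treadmill test at 4 of 4 visits (text for visits 1 and 2; text and Table 1 for visits 3 and 4).
4. Food: none described between arrival and the test.
5. Relaxation: a lapse in preparation before one visit is not a deviation. The reason given is consistency of testing. Nothing directs anyone to eat or to change a dose. Read literally, it covers a single visit. The comparable relaxation for the 48-hour treatment interruption, later in the same section, has no such limit.

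Items 1 to 4 together allow the sequence of drug, no food and exercise. Item 5 tolerates an occasional departure but does not address the patients concerned.

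**Visit 1.** Table 1 places consenting at visit 1. A patient might not have been asked to fast before that session, so exposure there is uncertain. Visits 2 to 4 do not have this uncertainty.

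**Scheduled tests**

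- Patients: 4 + 4 = 8 (section 4.0).
- Tests per patient: 1 (visit 1) + 3 (visits 2 to 4) = 4, or 3 if visit 1 is left out.
- Tests in the trial: 8 × 4 = 32, or 8 × 3 = 24 without visit 1.
- With k affected patients who follow the instructions and take the drug: up to 4k of 32, or 3k of 24.

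| k (assumed) | Visits 1 to 4 | Visits 2 to 4 only |
|---|---|---|
| 0 | 0 of 32 | 0 of 24 |
| 1 | 4 of 32 (12.5%) | 3 of 24 (12.5%) |
| 4 | 16 of 32 (50%) | 12 of 24 (50%) |

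The share is k/8 in either column, because 4k/32 = 3k/24 = k/8. The table therefore adds nothing beyond the assumed k, which the documents do not supply; the rows illustrate and do not bound it. The figure that can be read from the protocol is 3 or 4 tests per affected patient. These are scheduled occasions, not probabilities of harm.

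**The case against.** The strongest reply is that the protocol obliges nobody to do this. Fasting is requested and described as desirable, medication is only permitted, and a patient who holds or adjusts a dose is also within the rule. That is correct. A reader might infer that the protocol instructs patients to take insulin unfed, and the text does not support that. What stands is that a patient who does what is asked and what is allowed may arrive at that combination, and nothing in the rule steers them away from it.

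A second reply is that practical advice may sit elsewhere. Section 4.0 promises participants detailed instructions on the set-up and measurements, and the consent pages are not available for review. It would be wrong to infer that patients receive no advice. The point is confined to the rule written in section 5.0.

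Third, there are general safeguards. Exclusion criterion 7 lets the investigator decline a patient whose condition makes participation unsuitable, and a cardiologist is present in the Heart Station during the day. The first governs entry and gives an enrolled patient no dosing guidance. The second helps once an event has happened. Both lower the residual risk without changing the rule.

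Fourth, a remedy can do harm of its own. Holding all insulin by default would include long-acting background insulin and could lead to high glucose. Widening the existing relaxation from one visit to any visit would also loosen the tobacco, alcohol and exercise instructions for all 8 patients. Both objections are sound, and they limit what should be changed.

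**Conclusion.** The point holds as a low-severity safety matter worth considering. The preparation rule has no exception for a drug class that needs one, and a treadmill test follows at visits 2 to 4, and at visit 1 if the fasting request reaches the patient in time. An affected patient faces 3 or 4 such tests.

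This rests on two assumptions: that at least one enrolled patient uses insulin or an insulin-releasing drug, and that this patient fasts and takes the dose. The eligibility criteria allow the first, but the documents give no number, and it may be 0 of 8.

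A reader might go further and infer that harm is likely, or that the treadmill results would be distorted. The documents contain nothing from which either could be estimated, and neither is claimed.

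**What to change.** In section 5.0, replace the medication sentence with wording such as:

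*Subjects may take their usual morning medication, except that subjects on insulin or drugs that stimulate insulin release will follow the treating clinician's direction on dose timing or adjustment and on eating before the session; eating on such advice is not a protocol deviation at any visit, whether the subject ate is recorded, and the same approach is used at each visit where possible.*

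This leaves the choice between adjusting the dose and eating to the clinician, so background insulin is not held by default. Leave the existing one-visit wording unchanged for tobacco, alcohol and exercise. Add low glucose to the treadmill paragraph under Potential risks to subjects. If participant instructions already cover this, only the protocol text needs aligning with them.

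The cost is one replaced sentence and one added risk, with no new visit, window or mandatory test. In affected patients a few tests may not be fasted, or a dose may be delayed on up to four mornings. Sessions are stated to last about 3 hours at visit 1 and 4 hours at visit 2; any delay also includes the time between the usual dose and arrival, which the documents do not give. Recording food intake and keeping the approach constant within a patient limits the loss of consistency.

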**Potential risks to subjects:**

***Treadmill Cardiopulmonary Exercise Test:*** Intervention trials in PAD have demonstrated the ability of the graded treadmill exercise test to safely and robustly quantify changes associated with efficacious interventions (3). This test has been shown to be very safe, even in populations with underlying high-risk cardiovascular diagnosis (8), including patients with PAD (1). However, there is a chance that patients may experience chest pain, intolerable dyspnea, leg cramps, staggering, diaphoresis, and dizziness. The Treadmill Test will be conducted in the Heart Station where a Cardiologist is present 8AM to 5PM daily. Participants with an abnormal baseline treadmill stress test, including signs of coronary ischemia and an exaggerated pressor response, will be excluded from the study.

***IPC:*** There are no known side effects to IPC. It has been reported that patients with severe PAD may experience pain during initial exposure to the treatment.

**Venous blood sampling:** During blood sampling there is a risk of pain from the needle. Bleeding, local swelling, bruising and formation of a hematoma might also occur around puncture site.

**Measurement of calf muscle oxygenation:** There are no risks associated with calf muscle oxygenation measurements.

**Rest pain measurement:** There are no risks associated with rest pain measurements.

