## **7.0 Study Withdrawal/Discontinuation**

Participation in this study is voluntary. Participants may choose not to participate or, if they agree to participate, they can withdraw their participation at any time without penalty or loss of benefits to which they are otherwise entitled.

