## **8.0 Statistical Considerations**

The results obtained in this pilot experiment will allow us to demonstrate the feasibility of recruitment, randomization and intervention implementation and will provide the necessary data to support pursuit of a larger randomized clinical trial. Walking tolerance, limb hemodynamics and muscle oxygenation parameters will be compared between groups with two-way repeated-measures ANOVA, followed by Tukey's post hoc test when appropriate. We estimate that 4 subjects per group are needed to show feasibility and to provide support to our hypothesis that repeated exposure to IPC improves leg hemodynamics and reduces leg pain in patients with severe PAD recovering from peripheral revascularization.

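### The plan does not say that patients who stop the device are still measured, and its repeated-measures ANOVA conventionally drops anyone with a missed visit

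*Combined protocol and SAP*

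**What the plan says.** The follow-up visits are described in three ways.

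- Section 2.0 (Rationale and Specific Aims): "Prior to the onset of the treatment and 1 and 3 months after daily home-based IPC".
- Section 4.0 (Enrollment/Randomization): "Outcomes will be reassessed 1 and 3 months after the onset of home-based treatment".
- Section 5.0 (Study Procedures): "Outcomes will be reassessed after 1 month of treatment (end of week" 4, ± 7 days), and then "at the completion of the intervention (end of week" 12, ± 7 days). Table 1 labels visits 3 and 4 as 1 month and 3 months.

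Both groups are asked to "use the device while seated for 2 hours daily for 3 months". Section 5.0 classes 3 consecutive missed treatments, or 8 or more in total, as a protocol deviation. It does not say whether outcome visits continue for such a patient. Section 7.0 (Study Withdrawal/Discontinuation) covers only leaving the study: participants are told that "they can withdraw their participation at any time without penalty". Section 8.0 says that walking tolerance, limb hemodynamics and muscle oxygenation will be "compared between groups with two-way repeated-measures ANOVA". It names no analysis set and no rule for missing visits.

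**The concern.** Consider a patient who puts the cuffs away at week 5. Section 4.0 and the week numbers in section 5.0 both point to a final visit near week 12. The treatment-based words in section 5.0 can be read as applying only to someone still under treatment, and the request there to pause the device for 48 hours before each outcome session also presupposes continued use. Site staff have no instruction for this patient.

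If the visit is not held, the conventional repeated-measures ANOVA needs all three time points, so the patient's baseline and 1-month data are lost as well. At 4 per arm, each such loss is large.

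The loss may also be related to treatment. The arms receive 120 and 30 mmHg, and the risk section reports that "patients with severe PAD may experience pain during initial exposure to the treatment". Exclusion criterion 11 in section 3.0 names increased pain while the device is running, which can be seen only once it is in use; the plan does not say what follows if this appears after randomisation. A comparison restricted to patients who tolerated their device is no longer a comparison of the randomised groups, and this pilot's estimates are meant to support a larger trial.

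**Working it through.** **1. Do the timings agree?** End of week 4 is day 28, so the window is days 21 to 35; one month is 365.25/12 = 30.4 days. End of week 12 is day 84, so the window is days 77 to 91; three months is 365.25/4 = 91.3 days, at the upper edge. For a patient who completes the planned treatment, all wordings describe essentially the same visits. For a patient who stops early, the week numbers still give a visit, and the phrase about completing the intervention does not clearly do so. Section 5.0 does not name the day from which its weeks are counted.

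**2. The plan's own figure.** The 4 per group in section 8.0 cannot be reproduced: no effect size, SD, significance level, power or dropout allowance is given. Only the effect of a loss can be checked.

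**3. Cost of one loss.** One patient of 4 is 25% of an arm. With common SD σ, the standard error of a difference is σ√(1/n₁ + 1/n₂).

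| Patients analysed | SE (in σ) | Ratio to 4 v 4 |
|---|---|---|
| 4 v 4 | √(1/4+1/4) = 0.707 | 1.000 |
| 3 v 4 | √(1/3+1/4) = 0.764 | 1.080 |
| 3 v 3 | √(1/3+1/3) = 0.816 | 1.155 |

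In data points, 8 patients × 3 time points = 24 values. One missed final visit leaves 23 observed, but a complete-case ANOVA uses 7 × 3 = 21, so two observed values are discarded.

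For illustration, assume a single two-sided 5% t comparison at 3 months and a true difference of 2 SD. Noncentral-t power is then 66% at 4 v 4 and 56% at 3 v 4.

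**4. How likely is a stop?** The documents give no rate. With an assumed risk p per patient, the chance of at least one stop among n patients is 1 − (1 − p)ⁿ.

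| Assumed p | One arm (n = 4) | Trial (n = 8, same p in both arms) |
|---|---|---|
| 5% | 18.5% | 34% |
| 10% | 34% | 57% |
| 20% | 59% | 83% |
| 30% | 76% | 94% |

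These are chances of stopping the device. They become chances of losing a visit only if stopping leads to a missed visit, which the plan leaves open.

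**5. Possible bias.** Suppose the lost patient changed 1 SD less than the other three in the arm, whose mean is m. The mean of four is m − 1/4 SD and the mean of three is m, so the arm mean moves by 0.25 SD. If the lost patient is always the worst of four normally distributed values, simulation gives a shift of about 0.34 SD. Against the 4 v 4 standard error of 0.707 SD, these are 0.25/0.707 = 0.35 and 0.34/0.707 = 0.48 of a standard error.

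Direction depends on the assumption. With a 10% stopping risk in both arms, each arm has a 0.24 chance of being the one that loses more patients. With 30% active and 10% sham, the chances are 0.60 for active and 0.11 for sham.

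**The case against.** The strongest reply is that the sentence in section 5.0 does not stop at completion of the intervention. It fixes the visits at weeks 4 and 12, Table 1 agrees, and nothing in the plan cancels a visit because the device was put away. That stands. A reader might infer that sections 4.0 and 5.0 contradict each other, and that a patient who stops has no final visit under section 5.0; the text does not support this. Any loss would come from the plan's silence, not from a rule in it.

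A reader might also infer three further things that the documents do not establish.

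- **That stopping will be commoner in the 120 mmHg arm, so that the result will favour IPC.** The pressures and the remark on pain make this plausible. But the remark concerns first exposure, it follows a statement that IPC has no known side effects, and no tolerability or stopping figure is given for either arm.
- **That the rest-pain comparison is distorted by the ANOVA.** Rest pain is not among the outcomes that section 8.0 lists for that analysis.
- **That retention cannot be told apart from treatment completion.** Section 5.0 tracks compliance separately, through weekly calls, a timer in the unit and defined deviations.

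It is also fair to say that this is a pilot aimed largely at feasibility, that a deletion rule is the convention for this ANOVA rather than something section 8.0 states, and that a mixed model on 8 patients has little data from which to estimate a covariance. The last point limits which model is sensible. None of these points tells staff what to do with a patient who stops, or the analyst what to do with a missing visit.

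**Conclusion.** The concern holds as a gap and an ambiguity. Three sections describe the visits differently, none says that a patient who stops the device is still measured, and the named analysis conventionally excludes anyone with a missing visit. The firm part of the size is arithmetic: one excluded patient is 25% of an arm and adds about 8% to the standard error, and one per arm adds about 15%. The chance of a stop and the 0.25 to 0.34 SD shift rest on assumed rates and assumed prognosis. A biased comparison is therefore possible, but its size and direction cannot be stated from the documents. For a pilot of 8, the main harm is an unclear estimate and an unclear count of who was followed, not a wrong confirmatory conclusion. The correction is cheap enough to make before enrolment.

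**What to change.** - **Sections 2.0, 4.0 and 5.0:** use one time origin, the first home treatment. State that outcomes are collected at weeks 4 and 12 (± 7 days) whether or not the device is still in use, unless the patient withdraws from follow-up. This concerns measurement only, not who should stop or continue the device.
- **Section 7.0:** separate stopping the device (date and reason recorded, remaining visits kept) from withdrawing from follow-up. Report each by arm as a feasibility result.
- **Section 8.0:** replace the repeated-measures ANOVA with a mixed model on all randomised patients in their assigned group, with compound-symmetry covariance and small-sample degrees of freedom. It keeps patients with a missing visit and, with complete data and a non-negative between-patient variance estimate, matches the ANOVA. Show each patient's data as well.

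**Cost:** wording in these sections and no visits beyond those already planned. Data collected off treatment may dilute the estimated effect slightly. The model does not recreate a missed 3-month value and does not remove bias if missingness depends on unobserved outcomes, so holding the visits matters more than the choice of model.
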